#### 4.1.1 PROCEDURES

**Overview of RaPPID:** RaPPID was a multi-level program modeled after a successful de-prescribing initiative in one VISN. The program had 3 main components: (1) activation of VISN Pharmacy Executives (VPEs) and their subsequent activation of Clinical Pharmacy Specialist (CPS) providers at VA Healthcare Systems within their VISNs; (2) provider education with targeted academic detailing and notifications; and, (3) patient education. CPS providers are pharmacists with training and expertise in medication stewardship, quality improvement, and medication-use evaluation. Many CPS providers have a broad scope of practice that allows them to prescribe and de-prescribe medications, deliver provider and patient education, and provide professional-to-professional academic detailing, and they often work with other clinical providers and patients to improve appropriate medication use (29). PBM has successfully used CPS providers in several national medication safety initiatives. In RaPPID, PBM leveraged this national network of experienced CPS providers to undertake this initiative focused on safely de-prescribing PPIs. Specifically, PBM asked VPEs randomized to the intervention to identify local CPS providers to champion the program at their respective facilities. CPS providers were then be “activated” with a variety of standardized tools (see below). It is important to note that while PBM had extensive experience in conducting medication evaluations, RaPPID was novel in several ways: (1) it was randomized – PBM had experience conducting randomization in the context of research studies using similar tools, (2) it involved one of the most commonly prescribed medications in VHA – prior evaluations had been significantly smaller in scale; and, (3) it involved appropriate de-prescribing – prior de-prescribing efforts had focused on acute medication safety issues, where de-prescribing recommendations were less nuanced and less apt to cause harm (such as upper GI bleeding due to inappropriate de-prescribing of PPIs).

**Activation of CPS Providers:** CPS providers were “activated” with a variety of standardized tools, including: (1) the PPI Dashboard; (2) educational materials to help CPS providers promote RaPPID to PCPs and clinical staff at their facilities; and, (3) educational materials for patients who were de-prescribed, to provide guidance and support for managing bothersome symptoms in the period immediately after de-prescribing. The PPI Dashboard served several important purposes. It allowed the CPS providers to efficiently identify PPI de-prescribing candidates up to 4 weeks ahead of a scheduled primary care visit. It also allowed CPS providers to track patients who had been de-prescribed and monitor adoption of de-prescribing by individual providers. Data on adoption allowed the CPS providers to deliver academic

detailing (using local and regional academic detailing resources managed by PBM) to providers who appeared to be slow to adopt de-prescribing recommendations.

**RaPPID De-Prescribing Regimen:** The RaPPID de-prescribing regimen varied according to whether the Veteran was receiving once-daily or twice-daily PPI therapy. For patients on twice-daily PPI, the dosing frequency was reduced to once-daily and maintained at that dose (i.e., 50% dose reduction). For patients on once-daily PPI, the dose was to first be tapered to once-daily PPI every other day for 2 weeks, followed by discontinuation. All patients were to be prescribed H2RAs to be taken as needed for intermittent upper GI symptoms. Written educational information regarding de-prescription was to be provided to patients by the primary care team. The recommended de-prescribing regimen and appropriate management of recurrent symptoms was a key component of provider and patient education and (as needed) academic detailing.

**Deployment of RaPPID:** CPS providers used a variety of methods to initiate contact with PCPs at healthcare systems within VISNs randomized to RaPPID, including direct contact at primary care staff meetings and electronic contact via email. PCPs were to be educated and trained on: (1) the scientific justification for RaPPID; (2) VHA's national commitment to the program; (3) the protocol for de-prescribing; and, (4) resources for Veterans who are de-prescribed (educational materials, consultation with CPS providers). CPS providers adapted (as needed) standardized educational materials to their local sites and worked with primary care leadership at their sites to devise efficient methods for disseminating these materials (e.g., during team meetings). Additionally, the VHA National Program Office for Gastroenterology notified VHA GI Section Chiefs and providers of the effort as part of national field calls and email listserv updates. Once RaPPID was deployed, CPS providers used the Dashboard to identify and track candidates for de-prescribing and notified PCPs of candidates using locally adapted approaches (e.g., note in CPRS, email).

#### 4.1.2 PROVIDER EDUCATIONAL MATERIAL EXCERPT

The text and table below were part of the educational materials for Pharmacy and Primary Care providers.

It is recommended that patients meeting inclusion-exclusion criteria should be deprescribed using one of the methods below. Some patients with GERD are expected to have recurrence of frequent bothersome symptoms intermittently in the coming months or years. Studies have suggested such patients can be well-managed by intermittent courses of once-daily PPI for up to 4 weeks. On-demand PPI therapy (in which the patient takes PPIs as they determine is needed based on symptoms and response) is also shown to be well accepted by patients with GERD. Only a minority of GERD patients should require daily maintenance PPI therapy to provide acceptable symptom relief.

Patients Taking PPIs	
Once Daily	Twice Daily

▪ Taper to every other day for 2 weeks and then discontinue

▪ Prescribe H2-receptor antagonists (e.g., famotidine, ranitidine) to take as needed for intermittent recurrent symptoms

	

▪ Taper to once daily PPI, taken 30-60 minutes before a meal

Patients should be cautioned that they may have rebound symptoms for a few weeks after discontinuation.	

## 4.2 JUSTIFICATION FOR INTERVENTION

Proton pump inhibitors (PPIs) are among the most commonly prescribed medications in the Veterans Health Administration (VHA), accounting for over 11 million 30-day prescriptions and nearly \$50 million in medication costs annually. Though effective for treatment of acid-related disorders such as gastroesophageal reflux disease (GERD), PPIs have been associated with possible harms in observational studies (e.g., enteric infections such as *Clostridium difficile* colitis, pneumonia, chronic kidney disease, fractures, dementia) (1,2), and a 2017 VA study reported increased mortality in Veterans receiving PPIs (3). Unfortunately, PPIs continue to be used without an appropriate indication or for longer and at higher doses than necessary (4,5). Accordingly, in 2019, VHA Pharmacy Benefits Management Services (PBM) deployed the Randomized PPI De-Prescribing (RaPPID) Program – a national, multi-level PPI de-prescribing initiative targeting patients for whom chronic PPI therapy may not be necessary. This program, modeled after a successful initiative in one VISN, was comprised of 3 key components: (1) activation of clinical pharmacy specialists; (2) provider education and targeted notifications and academic detailing; and (3) patient education.

RaPPID was among the largest concerted efforts at de-prescribing ever undertaken in VHA. Prospective evaluation of the program therefore presented a unique opportunity not only to enhance the program itself, but also to gain insights into how to reduce the use of low-value services more broadly, a key VHA priority for the coming decade. Indeed, estimates suggest that 10% of all healthcare spending in the U.S. pays for unnecessary care (6). But reducing the use of low-value care is challenging for many reasons. Programs to reduce low-value care often employ multiple interacting components, deployed in active healthcare delivery contexts, and they require patients, providers, and systems to “unlearn” well-established behaviors and expectations about healthcare delivery (7,8). These challenges are compounded when efforts are scaled to the level of an entire health system.

## 4.3 END-OF-STUDY DEFINITION

The end of the study is defined as completion of the 12-month follow-up period of the last enrolled subject.

# 5 STUDY POPULATION

## 5.1 INCLUSION CRITERIA

The target population was chronic proton pump inhibitor (PPI) users who had a scheduled primary care visit.

### Chronic PPI Users

Defined as: ≥90-day prescription during the 120-day period prior to a scheduled primary care visit

Patients Who Take PPIs	
Once Daily Meeting any of the following criteria:	Twice Daily Meeting any of the following criteria:

■ No clear indication for PPIs

■ Uncomplicated GERD (i.e., no erosive esophagitis, stricture, dysphagia, or Barrett's esophagus)

	

■ No clear indication for PPIs

■ Any indication (except Zollinger-Ellison)

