## 1.2 SCHEMA

Months 1-11

Validate PPI Dashboard Algorithm & Test User Interface  
Develop Educational Materials

Randomize

Intervention  
N = 9 VISNs

Control  
N = 8 VISNs

Month 12

Activate VISN Pharmacy Executives, Clinical Pharmacy Specialists & Academic Detailers  
Make Dashboard Available to Intervention Sites

Months 12-24

Electronically Enroll Patients in Dashboard  
Send Baseline Surveys to Patients of 2 VISNs (1 from each arm)

Months 15-27

Send 3-Month Follow-up Surveys to Patients of 2 VISNs (1 from each arm)

Months 24-36

12-month Follow-up of Enrolled Patients

Months 36-42

Data Analyses

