## 4 STUDY DESIGN

### 4.1 OVERALL DESIGN

**Study Design:** We evaluated RaPPID in the context of a nationwide, stratified cluster-randomized controlled trial that incorporated assessments of both effectiveness and implementation (hybrid type II) (28). RaPPID was a multi-level de-prescribing program modeled after a similar initiative developed and deployed in one VISN in 2015. After validating and testing the deprescribing algorithm and dashboard, developing educational materials and randomization (months 1-11), the program was deployed nationally in a cluster-randomized fashion (months 12-24). During the randomization and subsequent follow-up period (months 24-36), we assessed the program's impact on a variety of clinical outcomes.

**Study Population and Sample:** De-prescribing of PPIs has potential clinical and economic benefits (by reducing unnecessary daily use of a medication with possible long-term harms). However, de-prescribing may also be harmful due to worsening upper GI symptoms and increased risk of upper GI bleeding. To maximize potential benefit and minimize potential harm, RaPPID focused on “chronic PPI users” (defined as daily PPI for  $\geq$  90 days during the 120-day period prior to PCP visit) with uncomplicated GERD, OR with no clear indication for PPI. Those who had acceptable indications for chronic PPI therapy (e.g., NSAID use, anti-thrombotic use, PUD, Barrett’s esophagus, erosive esophagitis, eosinophilic esophagitis) were excluded. Identification of candidates for appropriate de-prescription was facilitated by a high-specificity electronic algorithm, as discussed in Section 2.2, Background.

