## 5.2 EXCLUSION CRITERIA

The RaPPID Program avoided de-prescribing PPIs in patients for whom chronic PPI therapy was recommended by guidelines, consensus statements, and/or expert opinion. Stopping PPIs in these patients could have caused harms such as upper GI bleeding. Patients taking PPIs were excluded from the dashboard if they had one or more of the characteristics listed in the table below.

Twice-daily PPI Users with Zollinger-Ellison	
Once-daily PPI Users with any the following characteristics:	

■ Eosinophilic esophagitis

■ Esophagitis

■ Barrett's esophagus

■ Peptic ulcer

■ Zollinger-Ellison

■ Idiopathic pulmonary fibrosis

	

■ Pancreatic enzyme replacement

■ Esophageal ulcer

■ Esophageal stenosis/stricture

■ Dysphagia (other than oropharyngeal)

OR	
NSAID Users Meeting any of the following criteria:	Low-dose Aspirin Users Meeting any of the following criteria:

■ age > 65 years of age

■ Take a 2nd NSAID

■ Take daily aspirin

■ Take an anti-thrombotic drug

■ Take an oral steroid

	

■ age <math>\geq</math> 60 years of age

■ Take NSAIDs regularly

■ Take an anti-thrombotic drug

■ Take a corticosteroid

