## 6 EXPERIMENTAL MANIPULATIONS

### 6.1 EXPERIMENT

Experiment: Behavioral	
Intervention Arm PPI De-prescribing Program	Control Arm Usual Care/No PPI De-prescribing Program

■ Alerts to clinical pharmacy specialists and primary care providers informing them of individual patients scheduled for upcoming primary care visits who meet criteria for PPI de-prescription

■ Activation of clinical pharmacy specialists

■ Education of primary care providers

■ Patient Education

	

■ Usual Care

■ Did not receive the national de-prescribing program

The study focused on the effect of the operational intervention, RaPPID, as compared to usual care. See Section 4.1.1 for detailed descriptions of intervention components.

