## 6.2 MEASURES TO MINIMIZE BIAS: RANDOMIZATION AND BLINDING

Randomization of VISNs (regions) was done by the study biostatistician. The investigators and operational partners were informed of the assignments after randomization was finalized.

There was no blinding once randomization was complete.

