## 6.3 PARTICIPANT WITHDRAWAL FROM THE STUDY & LOST TO FOLLOW-UP

Not applicable for RCT as all subjects electronically enrolled were analyzed.

For patient reported outcomes, we expected some missing data. Our initial analyses only used observed data, but for missing data for items within scales, we used recommended imputation strategies. For missing 3-month survey assessments, we used logistic regression with missing follow-up as a dependent variable to see if missingness is associated with baseline variables, including facility-level variables. We included baseline variables found to be predictive of missingness in the longitudinal data model, and if missingness was at random, longitudinal mixed-effects provided an unbiased estimate of the study group effect. If the extent of missingness is more than 20%, we conducted a secondary analysis by combining results based on multiply imputed data using sequential regression multivariate imputation method,

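### H1 patients are identified after unblinded VISN randomization by a rolling PPI-use rule that the program can influence, and no frozen-cohort check is planned

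*Combined protocol and SAP*

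**What the plan says.** - **Unit and timing.** Section 6.2 states that "Randomization of VISNs (regions) was done by the study biostatistician" and that blinding ended once this was done. Section 4.1 places randomization in months 1-11. The schema (Section 1.2) activates pharmacy executives, pharmacists and detailers at month 12 and opens the dashboard to intervention sites then. The step "Electronically Enroll Patients in Dashboard" covers months 12-24.
- **Entry rule.** Section 5.1 requires at least a "90-day prescription during the 120-day period prior to a scheduled primary care visit". It has separate columns for once-daily and twice-daily users: twice-daily users qualify with any indication except Zollinger-Ellison, while once-daily users need no clear indication or uncomplicated GERD.
- **Exclusions.** Section 5.2: "Patients taking PPIs were excluded from the dashboard if they had one or more of the characteristics listed in the table below". The listed esophageal and ulcer diagnoses apply to once-daily users.
- **Intervention.** Section 6.1 lists alerts tied to upcoming visits but also "Education of primary care providers". Section 4.1.1 adds staff meetings, email and academic detailing of slow adopters. The dashboard lets pharmacists "efficiently identify PPI de-prescribing candidates up to 4 weeks ahead of a scheduled primary care visit".
- **Endpoint and analysis.** H1 counts days prescribed at no less than the patient's baseline dosing frequency, for 12 months from the index visit (Section 8). Section 6.3, on withdrawal: "Not applicable for RCT as all subjects electronically enrolled were analyzed". The H1 model names arm, VISN random intercepts and randomization strata (Section 8.3). Section 8.2 names an ITT population without defining it.

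**The concern.** Whether a patient enters depends on PPI supply measured after the VISN was randomized and, for most patients, after the program started. PPI supply is also what the program is meant to reduce. Part of the intervention acts on providers rather than on one patient's visit, so it can act before a given patient is identified. Two routes follow:

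1. **Early stoppers.** A patient whose PPI is stopped well before the next scheduled visit no longer meets the rule and never enters the intervention cohort. The equivalent control patient stays in.
2. **Early step-down.** A twice-daily user stepped down before the index visit can be judged under the once-daily column. An indication accepted there as a reason for chronic therapy then removes the patient. A patient who still qualifies may enter with a once-daily baseline, so each later once-daily day counts toward the endpoint, whereas it would not count against a twice-daily baseline. The plan does not say at what date baseline frequency is fixed.

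Both routes remove or mis-score program successes in one arm only. The H1 difference would then be understated, in a design with little spare power. Analyzing everyone who enrolled does not recover patients who never enrolled, and neither do the listed covariates or the baseline comparisons.

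**Working it through.** **1. The plan's own power figure (Section 8.1.1).** Inputs: 17 VISNs, 10,563 candidates per VISN, ICC 0.12, two-sided 0.05.

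- Design effect = 1 + (10,563 − 1) × 0.12 = 1,268.4.
- Effective patients per VISN = 10,563 / 1,268.4 = 8.33.
- 70% vs 50% with 8 VISNs per arm: SE = √[(0.70×0.30 + 0.50×0.50) / (8×8.33)] = 0.083. Noncentrality = 0.20 / 0.083 = 2.41 on 14 df. Power = 61.0%, as stated.
- The four 25-point contrasts give 80.1-87.9%, all above 80%, as stated. With 9 vs 8 VISNs, 70% vs 50% gives 64.1%.

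The sample-size statement is sound and is not in question here.

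**2. When does a stop remove a patient?** The rule tolerates 120 − 90 = 30 uncovered days. A stop at the earliest dashboard notice, 28 days before the visit, leaves 120 − 28 = 92 covered days, so a continuously supplied patient still qualifies. Only a stop more than 30 days before the visit removes a patient. If visits are spread evenly over 365 days (assumption), (365 − 30)/365 = 92% fall more than 30 days after launch and (365 − 120)/365 = 67% have a lookback wholly after launch.

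**3. Size of the early-stopper route.** None of these inputs is in the documents except the 55% mean, which is the intervention value in the plan's 80% vs 55% contrast.

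- r = extra off-visit stopping per month in intervention VISNs: 0.25%, 1%, 2%.
- Lag = 1 month (step 2).
- m = mean share of PPI days that those removed would have had: 5-20%.
- f = average over t = 0 to 12 months of 1 − (1 − r)^max(t − 1, 0).
- Shift in observed intervention mean = (0.55 − f·m)/(1 − f) − 0.55.

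| r per month | f removed | Shift, m = 20% to 5% | Difference seen if truly 80 vs 55 | Power, 8 per arm (84.4% without bias) |
|---|---|---|---|---|
| 0.25% | 1.2% | 0.4-0.6 points | 24.6-24.4 | 83.2-82.6% |
| 1% | 4.9% | 1.8-2.6 points | 23.2-22.4 | 79.0-76.4% |
| 2% | 9.5% | 3.7-5.2 points | 21.3-19.8 | 72.4-66.1% |

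Example at r = 1%, m = 5%: (0.55 − 0.0489×0.05)/(1 − 0.0489) − 0.55 = 0.026.

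If instead a single 90-day fill anywhere in the window qualifies a patient, the lag could approach 4 months. At r = 1%, f is then 2.6% and the shift 0.9-1.3 points.

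**4. Step-down route.** If a share g of the intervention cohort is re-based to once daily and holds that dose for a share d of days, those patients contribute d instead of 0, and the mean rises by g × d. The documents give no share of twice-daily users, so this is not sized. Its direction is the same as in step 3.

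**5. Would freezing the cohort cost power?** Hardly, because the ICC dominates. If the cohort fell to about 30/365 of its size (868 per VISN), effective patients per VISN would go from 8.33 to 8.26 and power for 70% vs 50% from 61.0% to 60.7%.

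**The case against.** - **VISNs are analyzed as assigned.** A reader might infer that the arms compared are not the arms randomized. The documents do not support that: the H1 model keeps VISNs in their arms and adjusts for strata. What is unprotected is comparability of the patients within them.
- **Coding after an alert.** A reader might infer that providers recording an accepted indication after an alert remove continuing users and inflate the effect. Alerts concern patients already identified on the dashboard. The schema treats that as enrollment, and Section 6.3 says all enrolled patients were analyzed. No section says that the program changes diagnosis codes.
- **The stopping route is narrow.** This stands. The targeted elements are tied to visits, and action on the same visit leaves 92 covered days. Removal needs earlier, education-driven stopping, for which no rate is given. The 2% scenario implies 1 − 0.98^12 = 21.5% extra stopping in a year and is an upper bound for illustration.
- **The bias is conservative for H1.** This also stands for the early-stopper route: it pulls a superiority comparison toward no effect. It could still cause a missed or understated effect.
- **Step-down keeps patients on a daily PPI.** True for the 90-day rule. It does not address the change of eligibility column or of endpoint threshold.
- **A frozen cohort changes the question.** It keeps patients who stopped for other reasons or gained an exclusion before their visit, whom the program would not target, and it still needs a visit after launch. This is a good reason not to replace the primary cohort.
- **Counts by arm may exist.** The CONSORT diagram is not shown in the available text, so totals by arm may be reported there. The text plans no tabulation by month.

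**Conclusion.** The concern holds in a limited form. Patients are identified after unblinded randomization and activation, by a rolling rule on the behavior the program targets. The text fixes neither the cohort nor baseline dosing frequency before launch. Enrollment by algorithm limits discretion but does not help where the algorithm's inputs can be affected.

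The true size cannot be known from the documents. Under the assumptions in the working, the observed intervention mean rises by about 0.4-5.2 points against contrasts of 20-25 points, toward no effect on H1. The step-down route adds an unsized amount in the same direction. At the low end this is negligible. At the high end a true 25-point effect would be seen as about 20 points, near the contrast for which the plan itself reports only 61% power. A reader might extend the point to harms and utilization, but nothing in the documents allows that to be sized. This is a cheap improvement to the plan and does not invalidate the trial.

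**What to change.** 1. Keep the index-visit cohort as the primary H1 cohort.
2. Add a prespecified H1 sensitivity analysis. Apply the same algorithm in all 17 VISNs to CDW data frozen before deployment, fixing chronic use, exclusions and baseline dosing frequency at that date. Follow each patient from the first scheduled primary care visit after deployment, whether or not the rule is still met then.
3. Tabulate eligible counts and baseline dosing frequency by VISN, arm and calendar month. A fall in intervention VISNs that control VISNs do not show would be direct evidence of the problem.
4. State that the H1 conclusion will be qualified if the two cohorts disagree.

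If H1 has already been analyzed, the same work can be done as a re-analysis and labeled so. The cost is one more CDW query and a few lines of analysis plan. The power loss is under 1 point even for a much smaller cohort. The drawbacks are that the frozen cohort omits patients who become chronic users after deployment and includes some whom the program would not have targeted, so its contrast may be diluted.
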